### **9.3.2 Analysis of Secondary Efficacy Variables**

Change from baseline in the weekly average of the DSIS at Week 12: The change from baseline in the weekly average of DSIS at Week 12 will be analyzed similarly to the primary analysis as specified in Section 9.3.1.2. The model will include the change from baseline in weekly average of DSIS scores as the dependent variable; and fixed effects of treatment group, time (categorical), treatment group-by-time interaction, baseline weekly average of DSIS, baseline weekly average of DSIS-by-time interaction. The LS mean change from baseline at Week 12 for each treatment group will be presented with the corresponding SE and 95% CI. In addition, the LS mean change from baseline at each week will also be presented together with the corresponding SE and 95% CI by treatment group. The LS mean

change from baseline and SE at each week will also be presented in figure by treatment group.

The weekly average of DSIS will be calculated by averaging the non-missing DSIS scores at the baseline and in each week during the treatment period as defined in Appendix A. They will be calculated if there are at least 3 non-missing DSIS scores for each week, including the baseline. The DSIS scores collected up to treatment discontinuation will be used in the calculation of the weekly average of DSIS.

[figure not shown]
Proportion of subjects with  $\geq 30\%$ ,  $\geq 50\%$ , and  $\geq 70\%$  reduction from baseline in the weekly average of daily pain intensity on the NPRS at Week 12:

The percentage reduction in the weekly average of NPRS at Week 12 will be calculated as  $100\% \times (\text{weekly average at baseline} - \text{weekly average at Week 12}) / \text{weekly average at baseline}$ . The weekly average at baseline and at Week 12 are the scores used for the primary analysis.

Subjects with  $\geq 30\%$  reduction from baseline at Week 12 will be defined as “responders”. Subjects with  $<30\%$  reduction from baseline at Week 12 or subjects who discontinued treatment early will be defined as “non-responders”. Subjects who complete treatment but have missing weekly average at Week 12 will have the data imputed based on the last available weekly average and their response status will be determined based on the imputed score. The proportion of subjects with  $\geq 30\%$  reduction from baseline in the weekly average of NPRS at Week 12 will be summarized descriptively by treatment group.

The proportion of subjects with  $\geq 50\%$  and  $\geq 70\%$  reduction from baseline will be defined and summarized similarly.

Proportion of subjects categorized as much improved or very much improved at Week 12 on the PGIC assessment: The proportion of subjects categorized as much improved or very much improved at Week 12 on the PGIC assessment will be summarized descriptively by treatment group. Subjects who complete treatment but have missing data at Week 12 will have the data imputed from the last available measurement. Subjects who discontinue treatment will be considered as “non-responders”.

### **9.3.4        Multiplicity Adjustment**

There is no multiplicity adjustment for this Phase 2 study.

## **9.4        Safety Analysis**

The overall safety profile of VX-548 will be assessed in terms of the following safety and tolerability endpoints:

- Incidence of treatment-emergent adverse events (TEAEs)
- Clinical laboratory values (hematology, serum chemistry, coagulation, and urinalysis)
- ECG outcomes
- Vital signs

- Physical examination test values
- C-SSRS

All safety analyses will be performed based on the Safety Set based on actual treatment. In the unexpected scenario that a subject receives more than one treatment in the study, the following algorithm will be used to define actual treatment: for any dosed subjects, the actual treatment is defined as the VX-548 highest dose level among all received VX-548 treatment if the subject received any VX-548 treatment, regardless of the randomized treatment assignment; the actual treatment is defined as pregabalin if the subject did not receive any VX-548 treatment but did receive any pregabalin.

Only descriptive analyses of safety will be performed, and no statistical hypothesis testing will be performed.

#### **9.4.1 Adverse Events**

AEs will be coded according to MedDRA. For analysis purposes, AEs will be classified as pretreatment AEs and TEAEs as follows:

**Pretreatment AEs:** AEs that occurred before the first dose of study drug

**Treatment-emergent AEs:** AEs that worsened or started after the first dose of study drug through the end of the TE Period

For AEs with completely missing or partial start dates/times, if there is no clear evidence that the AEs started before or after the first dose of study drug, the AEs will be classified as TEAEs.

Imputation rules for missing or partial AE start dates/times are defined as Appendix D.

AE summary tables will be presented for TEAEs by treatment group, and will include the following:

- All TEAEs
- TEAEs by strongest relationship
- TEAEs by maximum severity
- TEAEs leading to treatment discontinuation
- TEAEs leading to treatment interruption
- Related TEAEs
- Serious TEAEs
- Related serious TEAEs
- TEAEs leading to death

Summaries will be presented by MedDRA SOC and PT using frequency counts and percentages (i.e., number and percentage of subjects with an event). When summarizing the number and percentage of subjects with an event, subjects with multiple occurrences of the same AE or a continuing AE will be counted once, and only the maximum severity level will

be presented in the severity summaries, and the strongest relationship level in the relationship summaries.

All AEs, including pretreatment AEs and TEAEs, will be presented in an individual subject data listing. In addition, listings containing individual subject AE data for TEAEs leading to treatment discontinuation, TEAEs leading to treatment interruption, SAEs and all deaths will be provided separately.

#### **9.4.2 Clinical Laboratory Assessments**

All statistical analyses of laboratory values will be performed using SI units. For treatment-emergent laboratory measurements, the observed values and change from baseline values of the continuous hematology, chemistry, and coagulation results will be summarized at each visit.

The number and percentage of subjects with selected test values meeting threshold analysis criteria during the TE period will be summarized. The threshold analysis shift from baseline criteria will also be summarized for selected chemistry measurements. The threshold analysis criteria are provided in [Appendix E](#).

Results of urinalysis and the urine/serum pregnancy test will be in individual subject data listings only.

In addition, listings of individual subject hematology, chemistry, and coagulation values outside the normal reference ranges will be provided. These listings will include data from both scheduled and unscheduled visits.

#### **9.4.3 Electrocardiogram**

For the treatment-emergent ECG measurements, a summary of observed values and change from baseline values will be provided at each visit and time point, as applicable, for the following ECG measurements: heart rate (HR; beats per minute [bpm]), PR interval (msec), RR interval (msec), QRS duration (msec), QT interval (msec), and QT corrected for HR intervals (QTcF [msec]).

The number and percentage of subjects meeting threshold analysis criteria during the TE period will be summarized. The threshold analysis criteria are provided in [Appendix E](#). A listing containing individual subject measurements meeting the threshold value criteria at any time point will be provided. This listing will include data from both scheduled and unscheduled visits.

In addition, the number and percentage of subjects by maximum treatment-emergent value of QT/QTcF intervals, categorized as  $\leq 450$  msec,  $> 450$  msec and  $\leq 480$  msec,  $> 480$  msec and  $\leq 500$  msec, and  $> 500$  msec, as well as maximum treatment-emergent change from baseline value of QT/QTcF intervals, categorized as  $\leq 0$  msec, and  $> 0$  and  $\leq 30$  msec,  $> 30$  and  $\leq 60$  msec, and  $> 60$  msec, will be provided.

Since ECGs are performed in triplicate, the mean of the ECG measurements will be used as the ECG value for summaries of observed values and change from baseline values, and all reported ECG measurements will be used to conduct threshold analyses and to assess maximum treatment-emergent values.

#### **9.4.4 Vital Signs**

For the treatment-emergent vital signs measurements, the observed values and change from baseline values will be summarized at each visit. The following vital signs parameters will be summarized: systolic and diastolic blood pressure (mm Hg), pulse rate (beats per minute), body temperature (°C), and respiratory rate (breaths per minute).

The number and percentage of subjects meeting threshold analysis criteria during the TE Period will be summarized. The threshold analysis criteria are provided in [Appendix E](#).

In addition, a listing containing individual subject vital signs values will be provided. This listing will include data from both scheduled and unscheduled visits.

#### **9.4.5 Physical Examination**

Physical examination (PE) results will be presented in an individual subject data listing only.

#### **9.4.6 Columbia-Suicide Severity Rating Scale**

The proportion of subjects with at least one event during the TE Period of suicidal ideation, suicidal behavior, suicidal ideation or behavior, or self-injurious behavior without suicidal intent, as recorded on the Columbia-Suicide Severity Rating Scale (C-SSRS), will be summarized. C-SSRS results for subjects with responses of "Yes" at any visit will also be presented in an individual subject data listing.

### **10 SUMMARY OF INTERIM AND IDMC ANALYSES**

Not applicable.

## 11 LIST OF APPENDICES

### Appendix A Analysis Visit Windows for Safety and Efficacy Assessments

Table 12-1 Analysis Visit Windows for Safety and Efficacy Assessments			
Assessment	Visit/Time point	Target Study Day /Time point per the protocol	Analysis Visit Window (in study days/time points)
Safety Assessment			
Hematology	Baseline	Day 1	[Screening Visit 1, Pre-dose Day 1]
Serum Chemistry	Week 3	Day 22	[Day 1 post-dose, 43]
	Week 9	Day 64	[44,74]
	Week 12	Day 85	[75,99]
Coagulation	Baseline	N/A	[Screening Visit 1, Pre-dose Day 1]
	Week 12	Day 85	[Day 1 post-dose, 99]
Standard 12-Lead ECG	Baseline	Day 1	[Screening Visit 2, Pre-dose Day 1]
	Day 1	Day 1	Nominal
	Day 1 2 hrs post-dose	Day 1	Nominal
	Day 1 4 hrs post-dose	Day 8	Nominal
	Week 1	Day 36	[Day 2, 21]
	Week 5	Day 36	Nominal
	Week 5 Pre-dose	Day 36	Nominal
	Week 5 2 hrs post-dose	Day 36	Nominal
	Week 5 4 hrs post-dose	Day 85	Nominal
	Week 12		[61,99]
Vital Signs	Baseline	Day 1	[Screening Visit 1, Pre-dose Day 1]
	Week 1	Day 8	[Post-dose Day 1,14]
	Week 3	Day 22	[15,29]
	Week 5	Day 36	[30,43]
	Week 7	Day 50	[44,57]
	Week 9	Day 64	[58,74]
	Week 12	Day 85	[75,99]
Efficacy Assessment			

**Table 12-1 Analysis Visit Windows for Safety and Efficacy Assessments**

Assessment	Visit/Time point 	Target Study Day /Time point per the protocol	Analysis Visit Window (in study days/time points) 
NPRS via daily e-diary	Baseline	N/A	[-7, -1]
	Week 1	N/A	[1, 7]
	Week 2	N/A	[8, 14]
	Week 3	N/A	[15, 21]
	Week 4	N/A	[22, 28]
	Week 5	N/A	[29, 35]
	Week 6	N/A	[36, 42]
	Week 7	N/A	[43, 49]
	Week 8	N/A	[50, 56]
	Week 9	N/A	[57, 63]
	Week 10	N/A	[64, 70]
	Week 11	N/A	[71, 77]
	Week 12	N/A	[78, 84]
Rescue medication via daily e-diary	Week 1	N/A	[1*, 7]
	Week 2	N/A	[8, 14]
	Week 3	N/A	[15, 21]
	Week 4	N/A	[22, 28]
	Week 5	N/A	[29, 35]
	Week 6	N/A	[36, 42]
	Week 7	N/A	[43, 49]
	Week 8	N/A	[50, 56]
	Week 9	N/A	[57, 63]
	Week 10	N/A	[64, 70]
	Week 11	N/A	[71, 77]
	Week 12	N/A	[78, 84]
PGIC	Week 1	Day 8	[Post-dose Day 1, 15]
	Week 5	Day 36	[29, 43]
	Week 12	Day 85	[78, 92]
	Safety Follow-up	N/A	Nominal

Notes: \* only include Day 1 post-dose measurements.

 Visit/time point names for analysis purposes are used to report data in tables and figures.

The analysis visit windows will be applied using the following rules for both scheduled and unscheduled visits:

[figure not shown]
- If no numerical measurement is available within a visit window, the measurement will be considered missing for the visit.
- If there is more than 1 numerical measurement available within the same visit window, use the following rules:

[figure not shown]
- i. The measurement closest to the target day/time point will be used; or
- ii. If there are multiple measurements within the same distance from the target day/time point, the latest measurement will be used.

[figure not shown]
For measurements collected on the date of the first dose of study drug, if it cannot be determined whether the measurement is before or after the first dose:

[figure not shown]
- a. If a scheduled measurement is pre-dose in the CSP, it will be treated as a pre-dose observation. If a scheduled measurement is post-dose in the CSP, it will be treated as a post-dose observation.
- b. Unscheduled measurements will be treated as post-dose observations.

When defining baseline for efficacy and safety, refer to the generic baseline definition in Section [9.1](#).

## Appendix C Imputation Rules for Missing Prior/Concomitant Medication Dates

Imputation rules for missing or partial medication start/stop dates are defined below:

1. Missing or partial medication start date:
  - a. If day is missing, use the first day of the month.
  - b. If day and month are both missing, use the first day of the year.
  - c. If day, month and year are all missing, use a date before the first dose date.
2. Missing or partial medication stop date and time:
  - a. If day is missing, use the last day of the month.
  - b. If day and month are both missing, use the last day of the year.
  - c. If day, month and year are all missing, assign ‘continuing’ status to stop date.

**Table 12-2 Prior and/or Concomitant Categorization of a Medication**

Medication Start Date	Medication Stop Date	
	< First Dose Date/Time of Study Drug	≥ First Dose Date/Time and ≤ End Date of TE Period
< First dose date/time of study drug	P	PC
≥ First dose date/time and ≤ end date of TE period	-	C

C: Concomitant; P: Prior

## **Appendix D Imputation Rules for Missing AE Dates and Times**

Imputation rules for missing or partial AE start dates and times are defined below:

### **If Hour and/or Minute of AE start time are missing, do not impute:**

- If the AE start date is before the first dose date, the AE will be classified as a pretreatment AE.
- If the AE start date is on or after the first dose date, the AE will be classified as a TEAE.

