13.1.1.3 Documentation of Adverse Events

All AEs will be collected from the time the ICF is signed until the following times:

- For subjects who do not enroll: until time of screen failure (e.g., screen failure, withdrawal of consent)
- For enrolled subjects who have a Safety Follow-up Visit: through the Safety Follow-up Visit
- For enrolled subjects who do not have a Safety Follow-up Visit, the earliest of
 - o 14 days after the last dose of tablet study drug, or
 - o the ETT Visit, if that visit is 14 days or later following the last dose of tablet study drug (see Section 9.1.4).

All subjects will be queried, using nonleading questions, about the occurrence of AEs at each study visit. When possible, a constellation of signs and/or symptoms will be identified as 1 overall event or diagnosis. All AEs for enrolled subjects will be recorded in the CRF and source document. AEs for subjects who are screened but not subsequently enrolled will be recorded only in the subject's source documents. The following data will be documented for each AE:

- Description of the event
- Classification of "serious" or "nonserious"
- Date of first occurrence and date of resolution (if applicable)
- Severity
- Causal relationship to study drug(s)
- Action taken
- Outcome
- Concomitant medication or other treatment given

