### **If Hour and/or Minute of first dose time are missing:**

- If the AE start date is before the first dose date, the AE will be classified as a pretreatment AE.
- If the AE start date is on or after the first dose date, the AE will be classified as a TEAE.

A missing or partially missing AE end date will not be imputed.

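### Parts of SAP Appendix D class an AE that began before first dose and worsened on study drug as pretreatment, which contradicts the TEAE definition in SAP 9.4.1 (minor)

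*SAP*

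**What the plan says.** SAP 9.4.1 sets up two classes. Treatment-emergent AEs are "AEs that worsened or started after the first dose of study drug through the end of the TE Period". Pretreatment AEs are "AEs that occurred before the first dose of study drug". The second definition does not exclude events that worsen later, so an AE that began in screening and worsened on drug meets both. The AE summary tables cover TEAEs only. Pretreatment AEs appear in the listing of all AEs, and SAEs and deaths have their own listings.

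For incomplete data, 9.4.1 points elsewhere: "Imputation rules for missing or partial AE start dates/times are defined as Appendix D". Appendix D opens with the same limited scope: "Imputation rules for missing or partial AE start dates and times are defined below". Its rules are:

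- Under the heading "If Hour and/or Minute of AE start time are missing, do not impute", the rule is "If the AE start date is before the first dose date, the AE will be classified as a pretreatment AE".
- Where the first dose time is missing, the same rule is repeated. Its companion reads "If the AE start date is on or after the first dose date, the AE will be classified as a TEAE".
- Where the day, or the day and month, of AE start is missing, a start date is imputed, in some cases with the help of the AE end date. It is then compared with the TE Period.
- Where the year is missing, the AE end date decides.

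None of these rules mentions worsening.

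Protocol 13.1.1.3 collects AEs from consent. Among the items recorded for each AE are when it first occurred and, if relevant, when it resolved. A date of worsening is not listed.

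**The concern.** For some AEs the SAP gives two answers. An AE that starts in screening and becomes worse on study drug is treatment-emergent under 9.4.1. If it is held on one record and its start time is blank, Appendix D says without exception that it is pretreatment. The overlap between the two definitions in 9.4.1 does not settle the matter, so a programmer is likely to follow Appendix D, which gives the more definite instruction.

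TEAE incidence is the first-listed safety endpoint in SAP 9.4. Events that are ongoing at Day 1 are plausible here. Screening can last 35 days (Protocol 9.1.1), or 42 with an extension (Protocol 9.1.1.4), and subjects come off their pain treatments during it (Protocol 9.4.1). If such an event gets worse on drug and is classed as pretreatment, it is missing from the TEAE tables by severity, relationship, seriousness and discontinuation. Those are the tables in which a worsening on drug should show.

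**Working it through.** The plan gives no figure to reproduce, so the check applies both sets of rules to one test event. The event starts before first dose, worsens on drug within the TE Period, ends after first dose and is kept on one record. For illustration, first dose is 15 March 2023 and the AE ends on 20 April 2023. These dates are invented.

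| Situation | SAP 9.4.1 | Appendix D | Conflict |
|---|---|---|---|
| 1. Start date and time complete (5 March), first dose time known | TEAE | Does not apply | No |
| 2. Start date complete (5 March), AE time missing | TEAE | Start date before first dose date: pretreatment | Yes |
| 3. Start date complete, first dose time missing | TEAE | Same rule: pretreatment | Yes |
| 4. Day missing, month of first dose (March 2023) | TEAE | AE not ended before first dose, so start set to first dose date: TEAE | No |
| 5. Day missing, earlier month (February 2023) | TEAE | Start set to 1 February, before the TE Period: pretreatment | Yes |
| 6. Day and month missing, year of first dose (2023) | TEAE | Start set to first dose date: TEAE | No |
| 7. Day and month missing, earlier year (2022) | TEAE | Start set to 1 January 2022: pretreatment | Yes |
| 8. Year missing | TEAE | AE end date not before first dose: TEAE | No |

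The rules conflict in situations 2, 3, 5 and 7, which is 4 of 8. This counts types of situation. It does not say how often each occurs.

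In situations 4, 6 and 8 the two agree for a reason unrelated to worsening: Appendix D presumes onset on treatment. Comparing 2 with 4 shows an odd result. For an event starting in the month of first dose, losing the day gives TEAE, while knowing the day but not the clock time gives pretreatment. The more complete record gets the less cautious class.

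In situations 2 and 3 the missing time leaves no doubt about onset, because the start date already lies before the first dose date. The rule is right that the event began before dosing. It goes wrong by turning that into a final class without asking whether the event worsened.

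The weight of one subject follows from the planned arm sizes (SAP Table 7-1): 1/50 = 2 percentage points in the high-dose, mid-dose and pregabalin arms, and 1/25 = 4 points in the low-dose arm. The row for any TEAE changes only if this was the subject's only TEAE. Otherwise only the rows for that event and its subset tables change.

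**The case against.** The best defence is that 9.4.1 is the governing definition and Appendix D is only a set of missing-data rules. That stands as to scope. A reader might infer that Appendix D sorts all AEs by start date alone, and the documents do not support this: complete records stay under 9.4.1, and three of the Appendix D rules use the end date. The defence does not remove the conflict, because the rules for missing times assign a final class and do not refer back to the worsening criterion.

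The second defence is about recording. Protocol 13.1.1.1 treats the worsening of an existing condition after consent as an AE. A post-dose worsening could therefore be entered as a new AE with its own start date, and Appendix D would then make it a TEAE. This would remove the problem wherever it is done. But neither document says that an AE already recorded in screening gets a new record when it worsens. The eCRF completion guidelines that would settle this are not among the documents, so the effect is conditional and not established.

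Third, the list in Protocol 13.1.1.3 gives dates without times, and a reader might infer that the missing-time rule would govern nearly every AE. The SAP speaks of AE start times down to the minute, which suggests that a time field exists. Nothing shows how often it is blank.

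Fourth, a reader might press the point that the missing-time rules set no end to the treatment-emergent window. This matters little. AE collection stops at the Safety Follow-up Visit or its equivalent (Protocol 13.1.1.3), later related SAEs go on the SAE Form (Protocol 13.1.2.2), and 9.4.1 itself stops at the end of the TE Period.

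Finally, no such event disappears from view, because the all-AE and SAE listings are not limited to TEAEs.

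**Conclusion.** The SAP is wrong as written, and the point is minor. In the four conflicting situations Appendix D and 9.4.1 give opposite classes to a screening-onset AE that worsens on drug and stays on one record. If Appendix D is followed, the event is left out of the TEAE summary tables and kept in the all-AE listing. Two programmers working from the same SAP could produce different tables.

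The conclusion rests on two conditions that the documents leave open: that the worsening is not entered as a separate record, and that the start time, the first dose time or part of the start date is missing in one of the ways shown.

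The number of subjects affected cannot be computed. A reader might try assumed rates, such as 10–20% of subjects with an AE ongoing at first dose and 5–20% of those worsening. That gives 175 × 0.10 × 0.05 = 0.9 to 175 × 0.20 × 0.20 = 7 subjects. The documents support neither rate, and the product also assumes that every such AE falls in a conflicting situation on a single record. It should not be quoted as an estimate. Efficacy results are untouched, and no hypothesis tests are planned for safety data.

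**What to change.** Make three changes before database lock:

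1. In Appendix D, add to the rules for a missing AE start time, a missing start day, a missing start day and month, and a missing first dose time: *unless the AE worsened on or after first dose and within the TE Period, in which case it is a TEAE (Section 9.4.1)*. Keep the imputation rules in force for all AEs, so that a worsened AE with a partial date still has a rule to follow.
2. In SAP 9.4.1, limit the pretreatment definition to AEs that did not worsen after first dose. This removes the overlap between the two classes.
3. In the eCRF completion guideline, state that a post-dose worsening of an AE already recorded is entered as a new record with its own start date. The protocol's list of AE items has no date of worsening, so without this the exception in Appendix D may have no data to act on.

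The cost is a few lines of SAP text and one line in the guideline. The downside is that a few more events will be counted as treatment-emergent, which is what the 9.4.1 definition already calls for.
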